### 8. RESEARCH QUESTION AND OBJECTIVES

The research question is: Is there evidence that prescribers in the EU are compliant with the recommendations and limitations for use described in the tofacitinib aRMM materials?

The primary objectives are to:

- 1. Describe the characteristics of patients treated with tofacitinib, stratified by study country (i.e., Sweden, Hungary, the Netherlands, and Germany) and indication (i.e., RA, PsA, and UC; off-label indications), in terms of:
  - Demographics (e.g., age, sex); and
  - Comorbidities and prior and current medication use.

<sup>b The 2021 signal evaluation procedure also required the evaluation of tofacitinib use in elderly patients aged  $\geq$ 65 years, however, this assessment had already been added to the protocol following the findings from the 2019 Article 20 referral.

- 2. Evaluate prescribers' adherence to the tofacitinib aRMMs, specifically:
  - Compliance to the recommended posology per indication (average daily dose [ADD]) and duration of use;
  - Compliance to patient screening and laboratory monitoring prior to and during tofacitinib treatment; and
  - Compliance to recommendations for limitations of use, including:
    - Use in patients with VTE risk factors;
    - Use in patients aged 65 years and older;
    - Use in patients with CV risk factors;
    - Use in patients with malignancy risk factors;
    - Contraindicated use; and
    - Use with concomitant medications not compatible with tofacitinib.

The secondary objectives are to:

- 1. Describe prescribing patterns over time; and
- 2. Describe changes in the utilisation of tofacitinib following the updated recommendations and limitations for use implemented after the 2019 Article 20 referral and the 2021 signal evaluation procedure, specifically:
  - Use in patients with VTE risk factors;
  - Use in the elderly (patients aged 65 years and older);
  - Use in patients with CV risk factors; and
  - Use in patients with malignancy risk factors.

**Note:** In Gesetzliche Krankenversicherung (GKV) claims (Germany), outpatient diagnoses are reported quarterly, which could result in the misclassification of baseline clinical characteristics and select outcomes of interest, impacting all objectives except for primary objective 2.

In the PHARMO Database Network, the high-budget impact medication dataset contains only declared medication for approved indications. It might not be possible to determine offlabel use in this dataset. The objectives and sub-objectives that contain an ADD component will *not* be assessed in Hungary or the Netherlands. The Hungarian administrative claims database is unable to estimate ADD, either directly or by proxy, due to how tofacitinib is captured in the database. In the high-budget impact medication dataset of the PHARMO Database Network (Netherlands), where tofacitinib use is captured, neither ADD nor the number of pills per prescription is captured.

The sub-objective that evaluates "prescribers' adherence to the tofacitinib aRMMs, specifically, compliance to patient screening and laboratory monitoring prior to and during tofacitinib treatment" will *not* be assessed in Sweden because the Swedish national health registers do not capture the laboratory tests of interest. In GKV claims, it may not be possible to differentiate an absolute lymphocyte count (ALC) laboratory test from an absolute neutrophil count (ANC) laboratory test, or an alanine aminotransferase (ALT) laboratory test from an aspartate aminotransferase (AST) laboratory test. In the PHARMO Database Network, tuberculosis (TB) screening and viral hepatitis B and C testing are not captured.

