Subsequently, in June 2021, as a result of a signal evaluation procedure (EPITT number 19382) to assess the increased incidence rate of major adverse cardiovascular events (MACE) and malignancies excluding non-melanoma skin cancer (NMSC) in patients treated with tofacitinib for RA, the European Medicines Agency (EMA) concluded that myocardial infarction (MI), lung cancer, and lymphoma were important identified risks. To minimise these risks, and the important potential risk of MACE and malignancies excluding NMSC, the EMA recommended that the SmPC be updated to include restrictions on use of tofacitinib in patients over 65 years of age, patients who are current or past smokers, patients with other CV risk factors, and patients with other malignancy risk factors (e.g., current malignancy or history of malignancy other than a successfully treated NMSC). In these patients, tofacitinib should only be used if no suitable treatment alternatives are available.

In conjunction with the initial authorisation in March 2017, to minimise important potential and identified risks associated with the use of tofacitinib and to continue to monitor important potential and identified risks, the Marketing Authorisation Holder (MAH) implemented an educational program designed to increase awareness of the risks of tofacitinib in each member state of the European Union (EU). This program consists of routine (i.e., SmPC and patient package insert) and additional risk minimisation measures (aRMMs; i.e., a prescriber brochure, checklists for treatment initiation and treatment maintenance, and a patient alert card to distribute to patients). There is also a website where healthcare professionals (HCPs) can access the aRMM materials.

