### 9.3.2. Variable definitions

Table 3 summarises and defines the study variables to be collected and analysed in the selected databases. Unless otherwise specified, these variables will be assessed during each patient's entire study period, baseline period, and follow-up period.

This study will use code-based algorithms from the literature (validated against a gold standard measure, where possible) and/or other code lists to identify study variables. All code-based algorithms and code lists will be reviewed and/or approved by the study sponsor

prior to study initiation. Preliminary algorithms and/or codes are proposed in the following table (see also ANNEX 3 through ANNEX 7). Final algorithms and/or code lists will be refined as part of the SAP development.

Where possible, operational definitions for the variables listed in Table 3 will be similar across the databases. Only ICD-10 diagnosis codes and procedure codes are referenced in Table 3; the specific coding systems used in each data source will be further described in the SAP. See Section 9.4 (Data sources) for a description of the selected databases and Section 9.9 (Limitations of the research methods) for a summary of the limitations associated with these databases.

Variable	Role	Operational definition		
Indication m				
Indication n	Indication (including potential off-label indications)	Reported in the following categories: RA, PsA, UC, and Other / unknown (i.e., potential off-label indications).		
		Defined as $\geq 1$ International Classification of Disease, 10 th Revision (ICD-10) diagnosis code for RA, PsA, or UC in the 12 months prior to and including the day of tofacitinib initiation. If there is no ICD-10 diagnosis code in the patient's data for RA, PsA, or UC during this time period, then the indication will be reported as Other / unknown. If a patient has multiple codes for any combination of indications (e.g., RA and PsA), the ICD-10 diagnosis code closest to the index tofacitinib prescription dispensing will be used to determine indication.		
Primary Objective 1: Demo	Primary Objective 1: Demographics, comorbidities, and prior and current medications m			

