Chronic kidney disease	Outcome: CV risk factor	Defined as ≥1 ICD-10 diagnosis code for chronic kidney disease while receiving tofacitinib.
Stable angina pectoris	Outcome: CV risk factor	Defined as ≥1 ICD-10 diagnosis code for stable angina pectoris while receiving tofacitinib.
Discontinuation of tofacitinib after developing ≥1 CV risk factors while taking tofacitinib	Outcome: CV risk factor	Defined as ≥1 CV risk factor while receiving tofacitinib therapy (as listed and defined above) PLUS 0 prescription dispensings for tofacitinib within a specific time window after the code for the CV risk factor.
		Note: The time window for when to look for a tofacitinib prescription dispensing will be specific to the CV risk factor acquired while receiving tofacitinib therapy and will be operationalized during SAP development.
		Duration of tofacitinib therapy defined in Section 9.3.3.
Continuation of tofacitinib after developing ≥1 CV risk factors while taking tofacitinib	Outcome: CV risk factor	Defined as $\geq 1$ CV risk factor while receiving tofacitinib therapy (as listed and defined above) PLUS $\geq 1$ prescription dispensing for tofacitinib within a specific time window after the code for the CV risk factor.
		Note: The time window for when to look for a tofacitinib prescription dispensing will be specific to the CV risk factor acquired while receiving tofacitinib therapy and will be operationalized during SAP development.
		Duration of tofacitinib therapy defined in Section 9.3.3.

 Table 3.
 Operational definitions of study variables in the selected databases

Variable	Role	Operational definition	
Analysis of malignancy ris	Analysis of malignancy risk factors in patients using tofacitinib y		
Assessment of malignancy re	Assessment of malignancy risk factors prior to initiation of tofacitinib		
Elderly at tofacitinib initiation (patients 65 years and older)	Outcome: Malignancy risk factor	Calculated as the date of tofacitinib initiation minus the patient's year of birth and reported in the following categories: $<65$ years and $\geq 65$ years.	
History of malignancy (non-metastatic and metastatic, excluding non- melanoma skin cancer)	Outcome: Malignancy risk factor	Defined as ≥1 ICD-10 diagnosis code for a malignancy (excluding non-melanoma skin cancer) in the 12 months prior to or on the day of the index tofacitinib dispensing.	

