Initiating tofacitinib with severe hepatic impairment aa	Outcome: Contraindicated use	Defined as ≥1 ICD-10 diagnosis code for severe hepatic impairment in the 12 months prior to and including the day of tofacitinib initiation.	
Initiating tofacitinib while pregnant	Outcome: Contraindicated use	Defined as tofacitinib initiation (i.e., the index date) occurring between the beginning and end of a pregnancy, as identified in the Swedish MBR and in the Perinatal Registry of the PHARMO Database Network (Netherlands) ; or as estimated using a combination of pregnancy-related diagnosis and/or procedure codes in the Swedish NPR, in NHIFA, the Hungarian administrative claims database, and in GKV claims (Germany).	
Receiving tofacitinib while pregnant	Outcome: Contraindicated use	Defined as evidence of a pregnancy while receiving tofacitinib therapy in the follow-up period, as identified in the Swedish MBR and in the Perinatal Registry of the PHARMO Database Network (Netherlands); or as estimated using a combination of pregnancy-related diagnosis and/or procedure codes in the Swedish NPR, in NHIFA, the Hungarian administrative claims database, and in GKV claims (Germany). Duration of tofacitinib therapy defined in Section 9.3.3.	
Initiating tofacitinib while having TB (active or latent) bb	Outcome: Contraindicated use	Defined as ≥1 ICD-10 diagnosis code for TB in the 60 days prior to and including the day of tofacitinib initiation.	
Initiating tofacitinib while having a serious and/or opportunistic infection	Outcome: Contraindicated use	
 
Defined as ≥1 ICD-10 diagnosis code for a serious and/or opportunistic infection in the 60 days prior to and including the day of tofacitinib initiation.
 
Complete list of serious and/or opportunistic infections in ANNEX 3.
 
LIST OF DIAGNOSIS CODES FOR SELECT INFECTIONS OF INTEREST.
 
	

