### 9.4.4. Germany: Gesetzliche Krankenversicherung (GKV) claims (SHI Database)

Germany has a multi-payer healthcare system consisting of a combination of statutory health insurance (SHI)—i.e., the Gesetzliche Krankenversicherung (GKV)—and private health insurance (PHI). GKV claims collects German healthcare data based on insurance claims from approximately 8-10 different SHI providers. Since an SHI is a requirement for individuals with a permanent place of residence in Germany, even for short-term stays, the general population coverage in the SHI is considered nationwide. The SHIs also allow insurance coverage for children and spouses within a family insurance policy. The population size available through this claims database is approximately 5 million individuals which represents an estimated 6.9% of the SHI-insured population in Germany and is nationally representative. Available data history reaches back to January 2011. In the database all individuals have a de-identified ID; therefore, longitudinal follow-up is possible. The database includes information on patient demographics and inpatient and outpatient care, as well as outpatient medical prescriptions. Available demographic information includes sex, age, insurance status, time insured, and region of residence. Inpatient and outpatient diagnoses are coded via International Classification of Disease, 10th Revision, German Modification (ICD-10-GM) codes and procedures are available. For outpatient diagnoses, only the quarter of the diagnosis is reported (i.e., the actual date is unavailable). Outpatient physician specialty information and inpatient medical department of care can be accessed. Medical prescriptions from retail pharmacies are coded using the ATC hierarchy and the date of the prescription dispensing is available. Information on patient anthropometric data (e.g., height, weight, body mass index [BMI]) is not available nor are result outcomes for laboratory tests (e.g., ALC, blood lipid levels) or clinical measurements (e.g., blood pressure).

Data for the previous year are updated in the 3rd quarter of the following year, implying a 9--12-month lag for data availability. Furthermore, IQVIA cannot access the data directly and must secure access through a partner, which can take an additional 4-5 months.

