The use of automated health databases for research has limitations, particularly regarding potential misclassification of the treatment and outcome variables. For example, the Swedish national health registers have minimal capture of inpatient hospital medication administrations and prescription dispensings, and partial capture of outpatient hospital medication administrations (i.e., medications administered in outpatient clinics located in hospitals) and prescription dispensings; thus, biologics that are dispensed or administered primarily through hospital channels will be missed. The major limitation for GKV claims (Germany) is that diagnoses recorded in the outpatient setting are reported quarterly and the same date is assigned to all visits in the quarter. Thus, it might not be possible to determine the exact date of RA/PsA/UC diagnosis or the exact date of diagnosis for comorbidities and outcomes that are managed in the outpatient setting. In the PHARMO Database Network, the high-budget impact medication dataset contains only declared medication for approved indications. It might not be possible to determine off-label use in this dataset. Additionally, in Sweden, vaccinations are typically administered by a GP or at a vaccination clinic and thus are not likely to be captured in the national health registers. In the PHARMO Database Network (Netherlands), the Out-patient Pharmacy Database does not capture vaccinations. The number of analysable patients for a given outcome will be limited by the availability of patient data in the databases required to be linked for that outcome. In GKV claims, differentiating between live and non-live vaccines is not possible. Furthermore, while these databases provide detailed information on dispensed medications, actual use cannot be determined. Thus, it is possible that patients who have never used tofacitinib may be included in the cohort. This limitation is mitigated in part by the fact that, regardless of whether a patient uses the drug, all patients should receive the recommended screening tests prior to receiving a tofacitinib prescription. Additionally, in some analyses, the patient population will be restricted to patients with  $\geq 2$  to facitinib prescription dispensings to further assure actual use.

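### The protocol wrongly exempts primary objective 2 from the German quarterly-dating problem, fixes 60-day, 3-month and closest-code rules that undated outpatient codes cannot support, and gives 'history of malignancy' a 12-month reach.

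*Protocol*

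**What the plan says.** **Dating of German diagnoses.** The Notes in the Abstract and in Section 8 state that quarterly reporting of GKV outpatient diagnoses "could result in the misclassification of baseline clinical characteristics and select outcomes of interest, impacting all objectives except for primary objective 2". Section 9.4.4 describes the data: "For outpatient diagnoses, only the quarter of the diagnosis is reported (i.e., the actual date is unavailable". Section 9.9 calls this the major GKV limitation, adds that "the same date is assigned to all visits in the quarter", and extends it to comorbidities and outcomes managed in outpatient care.

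**Rules applied to those diagnoses (Table 3, Section 9.3.2).**
- Contraindicated use: a code for "TB in the 60 days prior to and including the day of tofacitinib initiation", and the same 60-day window for serious or opportunistic infection.
- VTE risk factors: MI in the 3 months up to index.
- Indication, when a patient has codes for more than one: "the ICD-10 diagnosis code closest to the index tofacitinib prescription dispensing will be used to determine indication".

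**Malignancy.** Section 7 gives the restricted group as patients with, for example, "current malignancy or history of malignancy other than a successfully treated NMSC". Table 3 defines the history variable as "≥1 ICD-10 diagnosis code for a malignancy (excluding non-melanoma skin cancer) in the 12 months prior to or on the day of" the index dispensing.

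**The concern.** Objective 2 answers the research question. If the Notes are taken at their word, the German results on contraindicated use and risk-factor use appear free of a dating error that the protocol elsewhere ties to those same results.

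The short windows are a separate difficulty. A calendar quarter is longer than 60 days and about as long as 3 months, so a quarter-dated code cannot be placed inside either window or reliably before index. An infection that follows the first dispensing within the same quarter may be counted as contraindicated initiation, which puts effect before cause. Under the closest-code rule, two indications coded as outpatient diagnoses in one quarter carry the same date, and the rule has no tie-break.

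For malignancy, a variable that stops at 12 months understates use in patients with a cancer history, the quantity that the restriction is about.

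**Working it through.** **1. The exemption against the rest of the protocol.** Section 8 lists use with VTE, CV and malignancy risk factors and contraindicated use under primary objective 2. The quarterly-reporting footnote is attached in Table 3 to the Primary Objective 2 heading (s) and to its VTE (v), CV (w), malignancy (y) and contraindicated-use (z) blocks. It is also attached to the matching outcomes in Section 9.3.1 (e) and to the Section 9.7.1.2 title (pp). The Notes and these footnotes cannot both be right.

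**2. Size of the short-window error.** The protocol gives no figure for this. Its sample-size figure reproduces (0.50 × 0.50 × 1.96² / 0.10² = 96.04, so 97) and is not in question.

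Assumptions: a 91-day quarter, with index day i = 0 to 90 equally likely and diagnosis days uniform in time. The protocol does not say which date a quarter receives, so first, middle and last day are each tried. Outpatient codes only.

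*60-day window, including the index day (61 days).* Summed over the 91 index days, true in-window diagnosis days = 91 × 61 = 5551.
- First-day dating: the index quarter is flagged when i ≤ 60, giving 61 × 91 = 5551 flagged days. In window: Σ(i+1) for i = 0 to 60 = 1891. After index: Σ(90−i) = 3660. Captured 1891/5551 = 34%; flagged but after index 3660/5551 = 66%.
- Last-day dating: captured 1830 + 61 = 1891, again 34%; none after index.
- Mid-quarter dating: captured 856 + 1830 + 795 = 3481, so 3481/5551 = 63%; 19% of flagged days are after index.
- Counting every quarter that overlaps the window: flagged (91 + 60) × 91 = 13741. All true cases are captured, but only 5551/13741 = 40% of flagged days are in the window and 4095/13741 = 30% are after index.
- Counting only quarters lying wholly inside the window: none qualifies, since 91 > 61.

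*3-month window (90 days plus index day).* True days 91 × 91 = 8281. First-day dating captures Σ(i+1) for i = 0 to 90 = 4186, so 51%; mid-quarter dating captures 75%. Counting overlapping quarters gives 8281/16471 = 50% in the window.

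*12-month window (365 days plus index day).* 88% with first- or last-day dating and 94% with mid-quarter dating.

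**3. Malignancy look-back.** The restriction in Section 7 has no time limit; the variable has 12 months. Stated data starts are 1958 for the Swedish cancer registry, January 2004 for NHIFA and January 2011 for GKV. From January 2011 to the earliest index date, April 2017, is 6 years 3 months.

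**The case against.** The strongest reply is that the dating limitation is disclosed: the footnotes sit on the affected outcomes and Section 9.9 names the problem. A reader might infer that German results would simply be taken as unaffected. The footnotes make that too strong, but they also show that the clause in the two Notes is wrong, and no SAP can make it right.

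Second, quarter-only dating is stated for outpatient diagnoses only, and the protocol does not give the outpatient share of MI or serious-infection codes. This stands: the percentages above apply to outpatient codes and are not error rates for the whole German result.

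Third, a reader might infer that all baseline look-backs fail. The 12-month result of 88-94% does not support that.

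Fourth, Section 9.9 concedes that cancers older than 12 months will be missed and warns that too long an interval has its own risk, and Section 9.3.2 leaves final algorithms to the SAP. So the malignancy point is a mismatch between a label and a restriction, and it is not concealed. One might want to put a percentage on the cancer history that is lost. The documents give no prevalence or incidence to do so, and Table 3 counts any malignancy code, so follow-up care for older cancer can still be picked up.

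Fifth, Table 10 lists 843 + 169 + 190 = 1202 indications for 1111 patients, and a reader might take the excess of 91 as ties. It is overlap accumulated over 2017-2019 and does not show codes within one quarter.

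**Conclusion.** The point holds in three bounded parts.

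- The exemption of primary objective 2 contradicts the protocol's own footnotes and limitations and should go.
- The 60-day, 3-month and closest-code rules cannot be applied correctly to GKV outpatient codes. Under uniform timing, and depending on the assigned date, capture is about 34-63% for 60 days and 51-75% for 3 months. With first-day dating, about 66% of codes flagged in the 60-day window follow index. The 12-month windows are modestly affected.
- 'History of malignancy' covers less than the restriction it represents. The direction is understatement; its size cannot be computed from the documents.

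The figures rest on uniform index and diagnosis days and on assumed date placement. They illustrate scale and do not predict the German results.

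**What to change.** 1. **Notes in the Abstract and Section 8.** Delete the exemption. State that every objective 2 outcome or stratum that uses a GKV outpatient diagnosis is affected. This includes ADD outcomes conditional on UC, ADD stratified by indication or VTE risk factor, and any laboratory outcome identified by a diagnosis code. Only outcomes built solely on dispensings, age or dated procedures are unaffected. A shorter sentence clearing ADD and laboratory outcomes as a class would be a new error, since Table 3 lets both draw on diagnosis codes.

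2. **60-day and 3-month windows in GKV.** Report exactly dated inpatient codes. For outpatient codes, report a lower bound that excludes the index quarter and an upper bound that counts every quarter overlapping the window. The lower bound is approximate for the 60-day windows: no whole quarter fits inside them, so part of the preceding quarter lies before the window.

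3. **Indication.** Report the number of GKV patients whose indication codes tie within a quarter.

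4. **Malignancy.** Beside the 12-month result, report a longer look-back of equal length in all reporting periods where the source holds it (NCR from 1958, NHIFA from 2004, GKV from 2011). Otherwise label the variable 'malignancy recorded in the prior 12 months'. No start date is given for the Dutch data, so the label may be the practical choice there.

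The cost is a wording change, extra columns for Germany and extraction of earlier years. Patients with less observable history than the longer look-back must be counted and shown. The descriptive design and sample size do not change.
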